8.2.6 Laboratory Methodology

PBMCs will be isolated from SmartTubes. γ -H2AX foci will be quantified in fixed PBMCs using flow cytometry. This work will be completed by the [name] Laboratory at Dana-Farber.

Total mRNA will be isolated from PAXgene tubes, using the commercial PAXgene Blood RNA kit. RT-PCR will be used to quantify expression levels of the 9 genes previously shown to be modulated by radiation exposure: *GADD45A*; *CDKN1A*; *PCNA*; *SGK*; *HSP132*; *DDB2*; *TNRFSF6*; *XPC*; and *SESN1*. This work will be completed by the [name] Laboratory at Lawrence Livermore National Laboratory.

Plasma flt3 ligand and serum amylase will be quantified using commercial kits. This work will be completed by the TransLab at Dana-Farber/Boston Children's.

8.3 Evaluation of NET Protein Expression

8.3.1 Sample requirements

Five unstained slides will be submitted once. Material obtained from biopsy to diagnose or treat recurrent disease will be submitted. If not available, material from biopsy/resection to obtain initial diagnosis of neuroblastoma will be submitted. If not available, material from resection of primary tumor during initial induction will be submitted.

Materials obtained during bone marrow biopsy or fine needle aspirate procedure are not acceptable to support this evaluation.

8.3.2 Sampling scheduling

Samples will be submitted once, after study enrollment.

8.3.3 Sample processing

No additional processing is required at the treating institution.

8.3.4 Sample labeling

Slides or slide box should be labeled with the patient's NANT ID number, the protocol number N11-01, and the date of biopsy/resection.

No other identifiers should be included on the label.

8.3.6 Laboratory Methodology

NET protein expression will be assessed by immunohistochemistry and scored semi-quantitatively as previously described.¹⁰⁵ If other promising proteins involved in MIBG transport

emerge, such as vesicular monoamine transporters (VMATs), then these proteins will also be quantified.

8.4 Evaluation of Automated MIBG Scoring System

¹²³I-MIBG scans from study entry and following course 1 of therapy will be uploaded to the NANT PACS system for all patients as part of planned central review. These images will also be forwarded to [name] at the University of Chicago for evaluation of computer-assisted MIBG scoring. The imaging group at the University of Chicago will not have access to MIBG scan reports from treating institutions or results of central review of scans. Following the study, the scores obtained using the computer-assisted platform will be compared to those assigned by treating institutions and/or by central review.

8.5 Evaluation of Circulating Tumor DNA

Patients who provided consent for optional evaluation of blood markers of radiation exposure and have remaining aliquots of plasma leftover after quantification of plasma flt3 ligand will be included in this evaluation of circulating tumor DNA. Aliquots will be transferred to the [name] laboratory at Dana-Farber Cancer Institute, cell free DNA extracted using standard techniques, and then sequenced using next generation sequencing techniques. As appropriate, droplet digital PCR (ddPCR) may also be used to obtain comparative pilot data for these two approaches. No additional samples need to be collected from patients to support this work.

9.0 CRITERIA FOR REMOVAL FROM PROTOCOL AND OFF STUDY CRITERIA

9.1 Criteria for Removal from Protocol Therapy

- a. Progressive disease
- b. Completion of planned therapy (maximum of two courses of therapy on this protocol for patients enrolling prior to Amendment 7A and a maximum of one course of therapy on this protocol for patients enrolling with Amendment 7A or later)
- c. Patient/parent withdrawal from therapy
- d. Unacceptable adverse events by protocol criteria or physician judgment
- e. Entry onto another therapeutic study and/or another anti-cancer therapy.
- f. Pregnancy

Patients who are off protocol therapy are to be followed until they meet the criteria for off study.

9.2 Off Study Criteria

- a. Death
- b. Lost to follow-up
- c. Patient/Parent withdrawal of consent.

10.0 STATISTICAL CONSIDERATIONS

10.1 Pick-the-Winner Design

Up to a total of 105 eligible and evaluable patients will be randomly assigned to one of the 3 MIBG arms. At completion of the study, the regimen with the highest observed response rate (by central review of response) after one course of therapy will be selected as the “winner” – i.e. the regimen that will be recommended as the MIBG backbone for future studies – provided that toxicity, tolerability, and other considerations confirm the feasibility of the regimen.

Two interim analyses for futility (to drop an inferior arm) will be undertaken: after 60 patients (approximately 20/arm) and after 81 patients (approximately 27/arm) have been randomized and completed at least one course and deemed evaluable for response. This analysis will be performed initially using site report of response. The following rule will be applied: if one of the arms is clearly inferior to the other two, then consideration will be given to dropping that single regimen. Study accrual will not pause while awaiting the results of any interim analysis (see below for modification per Amendment 7A). However, study accrual will be halted if needed to complete central review of response prior to dropping any regimen. The criterion to be used is based on Bayesian posterior probabilities (see Appendix VIII).

In addition, if one arm is dropped at the time of the 1st interim analysis, then after 35 patients have been randomized to each of the remaining arms and evaluated after the 1st course, we will compare these 2 remaining arms based on site report of response. If one arm is not clearly superior according to Bayesian posterior probabilities, accrual will continue until 42 evaluable patients per remaining arm have been randomized (yielding total sample of 104 patients in this scenario).

If neither futility rule is met, accrual will continue until 35 patients/arm are eligible and evaluable, for a total of 105 patients. With Amendment 7A, the design was modified to apply stochastic curtailment principles to permit early selection of a winner (see below). In order to account for potentially ineligible or inevaluable patients, a maximum of 115 patients are anticipated to enroll to yield 105 eligible and evaluable patients.

10.1.1 Amendment 7A – Dated 6-8-2017

The results of the 1st interim analysis were submitted to the independent DSMB on March 15, 2017, with the recommendation not to drop any arm at that time and to continue as planned - with one modification to the study design (addition of rules to permit early selection of a winner). This recommendation was accepted by the DSMB.

The proposed modification to the design involves applying “stochastic curtailment” at the time of the next interim analysis (after 81 patients). Specifically, after 81 patients have been evaluated, the Arm with the greatest observed response rate will be identified (designated here as Arm X). Under a variety of scenarios, exact calculations will be done to determine the probability (conditional on the observed data of the 1st 81 patients) that the observed response rate for Arm X will still be greater than the observed response rates for other 2 Arms after 105 patients have been enrolled and evaluated. If this probability (or more precisely, the probability across a variety of scenarios) is greater than 0.90, then accrual will be terminated with the conclusion that the true response rate for Arm X is higher than the true response rates for the other 2 Arms. See the Table below for skeleton of the table that will be created.

Table: Calculations* for the Probability that Arm X will Still have the Highest Observed Response Rate** at the End of the Trial with 35 Patients per Arm (given the Results of the 1st 81 Patients)				
p_x = True Probability of Response on Arm X	p=0.10=True Probability of Response on the 2 Other Arms	p=0.15=True Probability of Response on the 2 Other Arms	p=0.20=True Probability of Response on the 2 Other Arms	p=0.25=True Probability of Response on the 2 Other Arms
0.10				
0.15				
0.20				
0.25				
0.30				
0.35				

**i.e. that the Arm X observed response rate would be greater than the observed response rates of other 2 arms
 *Calculations are based on exact binomial probabilities

If this conditional probability is less than 0.90 for any one of the scenarios in which all 3 arms have the same true response rate (highlighted in the Table above), then the study will continue as originally planned – with the possibility that one arm will be dropped because its response rate is inferior to the response rates of the other 2 arms.

The table below summarizes the minimal impact of incorporating stochastic curtailment at this stage, on the overall probability of correct selection, for a variety of scenarios (in none of these scenarios is the probability of correct selection decreased).

Table: Probability* of Selecting the Correct Arm						
True Probability of Response for the 2 Inferior Arms	Without Stochastic Curtailment			With Stochastic Curtailment		
	Difference in True Probability of Response between Best Arm and the Other 2 (least favorable configuration)			Difference in True Probability of Response between Best Arm and the Other 2 (least favorable configuration)		
	+0.0	+0.05	+0.10	+0.0	+0.05	+0.10
0.10	1.00	0.676	0.855	1.00	0.705	0.875
0.15	1.00	0.627	0.818	1.00	0.658	0.827
0.20	1.00	0.599	0.780	1.00	0.622	0.814
0.25	1.00	0.592	0.770	1.00	0.608	0.788
0.30	1.00	0.583	0.736	1.00	0.607	0.777

*Probabilities of correct selection estimated by simulation, using same methods a results in the Appendix

Logistic Considerations for 2nd Interim Analysis: Study accrual will pause while awaiting the results of the 2nd interim analysis, until it is clear that 81 patients are “evaluable for response”. In addition, no final decision will be made to terminate accrual or drop an arm, until central review of response is completed.

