10.5 Sample Size and Study Duration

While we expect that both the vincristine/irinotecan and the vorinostat arms will demonstrate higher response rates compared to the MIBG-alone arm – and that the selection therefore will only involve those

two arms – we have included the MIBG-alone arm to calibrate the improvement and better understand the impact of these chemotherapy additions. However, for purposes of determining the number of required patients, we will consider that all three arms are candidates of selection (i.e. could result in the highest observed response rate). The number of patients (35 per MIBG regimen, if no arms are dropped as inferior) was calculated to ensure an 80% chance that the regimen with the highest response rate is selected – if in fact that response rate is at least 15% better than the other two (using the methods described by Sobel and Huyett¹¹⁴ and summarized by Bechhofer, Santner and Goldsman¹¹⁵). Because we have incorporated Bayesian criteria for dropping an inferior arm or stopping early, the power of correct selection and other design characteristics were determined by simulation (see Appendix VIII for more details).

Table A in Appendix VIII summarizes the probability of correct selection, the probability of dropping one arm for futility, the probability of dropping the superior arm for futility, and the average number of patients in the inferior arm.

Estimates of the number of available patients for this study are derived from previous ¹³¹I-MIBG studies at NANT ¹³¹I-MIBG institutions. Specifically, NANT01-02 accrued 50 patients with refractory disease over approximately 40 months of active patient recruitment. NANT04-06 accrued 26 patients with relapsed or refractory disease over the approximately 40 months during which that study was open. This accrual rate underestimates the number of available patients given that NANT04-06 was a phase I study that utilized a 3+3 dose escalation strategy and accrual was closed for a minimum of 6 weeks after the third patient at each dose level was treated. CHOP, Cincinnati Children's, UCSF, and the University of Michigan treat 25, 12, 12, and 7 patients per year on their respective expanded access ¹³¹I-MIBG protocols. Newer NANT MIBG centers now include Children's Hospital Boston, Cook Children's Hospital, Children's Hospital of Colorado, Hospital for Sick Children, and Seattle Children's Hospital. These newer centers will increase access to MIBG treatment slots.

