As we observe data (X responders out of n patients treated on each arm separately) then we incorporate these data into our distributions of the true response rate, p . We calculate a new distribution which incorporates both our prior belief (or assumptions) and the data we have observed. So now, after having some data, we have the following distribution for p :

$$p|X \approx \text{Beta}(\alpha + X, \beta + (n-X))$$

where the mean becomes $(\alpha+X)/((\alpha+X)+(\beta+(n-X))) = c[X/n] + (1-c)[\alpha/(\alpha+\beta)]$

and where $c=n/(\alpha+\beta+n)$ and the effective sample size is $\alpha+\beta+n = n+1$.

We call this our posterior distribution of p .

Since the data in the 3 arms of the study are independent and since we know the posterior distributions for each of the response probabilities, then it is easy to determine the posterior probabilities. For this design, instead of calculating the posterior probabilities, we simulated the distributions with 2,000 realizations for each comparison.

A.2.2 Dropping an Arm / Deciding that the Response Rate is Inferior

After 60 patients (and again after 81 patients, if necessary) we will determine:

- (a) $\Pr \{ p_B - p_A > 0.05 \mid X_A, X_B, n_A, n_B \}$ and $\Pr \{ p_C - p_A > 0.05 \mid X_A, X_C, n_A, n_C \}$ and
- (b) $\Pr \{ p_C - p_B > 0.05 \mid X_C, X_B, n_C, n_B \}$ and $\Pr \{ p_A - p_B > 0.05 \mid X_A, X_B, n_A, n_B \}$ and
- (c) $\Pr \{ p_B - p_C > 0.05 \mid X_C, X_B, n_C, n_B \}$ and $\Pr \{ p_A - p_C > 0.05 \mid X_A, X_C, n_A, n_C \}$.

If the 2 probabilities on any line above are both > 0.85 , then we will conclude that Arm A (based on line (a)) or Arm B (based on line (b)) or Arm C (based on line (c)) is inferior and based on this and other considerations, we will close this arm to future randomization. These probabilities were determined based on 2,000 simulations.

A.2.3 Deciding after 90 Patients that we have Sufficiently Strong Data to Stop and Pick the Best Regimen

If an arm is dropped after 60 patients, then we will compare the 2 remaining arms after each has 35 evaluable patients. Without loss of generality, we will assume that Arm A has been dropped. At that time, we will determine the posterior probabilities (where $n_C = n_B = 35$):

$$\Pr \{ p_C - p_B > 0.05 \mid X_C, X_B, n_C, n_B \} \quad \text{and} \quad \Pr \{ p_B - p_C > 0.05 \mid X_C, X_B, n_C, n_B \}$$

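### Amendment 7A's early-stopping rule can select a winner but cannot support a conclusion about true response rates, and its table prints gains in correct selection that the rule cannot produce

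*Combined protocol and SAP*

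**What the plan says.** Section 10.1 sets out a selection design: at completion "the regimen with the highest observed response rate (by central review of response) after one course of therapy will be selected as the" winner. Section 10.5 sizes it accordingly; 35 patients per arm "was calculated to ensure an 80% chance that the regimen with the highest response rate is selected", given a true advantage of at least 15 percentage points.

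Section 10.1.1 describes the Amendment 7A change as "addition of rules to permit early selection of a winner". At 81 patients (about 27 per arm) the leader is called Arm X, and exact binomial calculations give the chance that X still has the highest observed rate at 105 (35 per arm). Above 0.90, "accrual will be terminated with the conclusion that the true response rate for Arm X is higher than the true response rates" of the other two arms. The closing paragraph of the rule names the binding scenarios: "If this conditional probability is less than 0.90 for any one of the scenarios in which all 3 arms have the same true response rate", the study continues.

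A table then compares correct selection with and without curtailment, for inferior-arm rates of 0.10 to 0.30 and a best arm 0, 5 or 10 points better. The text calls the impact minimal and adds that "in none of these scenarios is the probability of correct selection decreased". The footnote reads "Probabilities of correct selection estimated by simulation, using same methods a results in the Appendix".

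**The concern.** There are two problems.

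**The conclusion.** The rule predicts whether an observed lead at 27 per arm will survive 8 more patients per arm. It can be met when no arm is truly better, because the binding scenarios assume exactly that. A trial stopped at 81 would therefore carry a stronger written conclusion than one completed at 105, where the plan only selects the arm with the highest observed rate.

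**The table.** It is the plan's evidence that a mid-trial design change costs nothing. In all ten informative cells the With column is higher than the Without column. Early stopping uses less data than the full trial, so gains of this size in the chance of picking the right arm are not expected.

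**Working it through.** **Inputs.** 27 per arm at the second look and 35 at the end, so 8 more each (Section 10.1). Threshold 0.90 in the equal-rate cells at 0.10, 0.15, 0.20 and 0.25 (Section 10.1.1). Prior Beta(0.2, 0.8) for each arm, i.e. mean 0.20 and effective size 1 (Appendix VIII, A.2.1). Drop rule at 20 and 27 per arm, then the two-arm comparison at 35 and 42 (A.2.2, A.2.3).

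**Stopping region.** With leads d1 and d2, the chance that X stays strictly ahead under a common rate p is the sum over i = 0 to 8 of b(i; 8, p) × B(i+d1−1; 8, p) × B(i+d2−1; 8, p), where b and B are the binomial mass and cumulative functions.

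- Leads of 3 and 3: 0.896 at p = 0.20 and 0.870 at p = 0.25, so no stop.
- Leads of 3 and 4: 0.979, 0.956, 0.933, 0.912, so stop. This is the smallest stopping lead.

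**What a stop says about true rates.** At 8, 5 and 4 of 27 the posteriors are Beta(8.2, 19.8), Beta(5.2, 22.8) and Beta(4.2, 23.8). The probabilities of being best are 0.78, 0.15 and 0.07. The probability that X beats the runner-up by more than 0.05 is 0.70. Keeping the same lead but moving X from 4 to 13 responders takes these from 0.93 down to 0.73 and from 0.78 down to 0.67.

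Enumerating all 28³ outcomes at 27 per arm (drop rule ignored):

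- Three equal arms at 0.10, 0.15, 0.20, 0.25, 0.30: the rule stops in 13%, 20%, 24%, 28%, 30% of trials. This is not a type I error, since the full trial also names a winner, but each stop would carry a false statement about true rates.
- Wrong arm among early stops, against final selection at 35 per arm (ties split): 21–39% v 39–48% for a 5-point advantage; 6–18% v 19–30% for 10 points; 1–7% v 8–16% for 15 points.

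So the rule is a sound selection shortcut. Only the conclusion attached to it is unsupported.

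**Cap on the gain.** Curtailment adds a correct selection only when it stops on the truly best arm and that arm would not have been sole leader at 35 per arm. Hence gain ≤ P(stop, X is best, X not strictly ahead at 35), whatever the tie rule.

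**Reproducing the table.** The recomputed columns below come from simulating the full design, with the same trials used with and without curtailment and final ties credited to the best arm. That tie rule is the one that reproduces the Without column. In the first row, splitting ties gives 0.606 and 0.808, and counting them wrong gives 0.537 and 0.762, against the printed 0.676 and 0.855.

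| Inferior rate, advantage | Without: printed | Without: recomputed | With: printed | With: recomputed | Printed gain (points) | Cap (points) |
|---|---|---|---|---|---|---|
| 0.10, +0.05 | 0.676 | 0.682 | 0.705 | 0.681 | 2.9 | 0.10 |
| 0.10, +0.10 | 0.855 | 0.857 | 0.875 | 0.856 | 2.0 | 0.11 |
| 0.15, +0.05 | 0.627 | 0.638 | 0.658 | 0.636 | 3.1 | 0.23 |
| 0.15, +0.10 | 0.818 | 0.815 | 0.827 | 0.813 | 0.9 | 0.23 |
| 0.20, +0.05 | 0.599 | 0.610 | 0.622 | 0.607 | 2.3 | 0.36 |
| 0.20, +0.10 | 0.780 | 0.786 | 0.814 | 0.783 | 3.4 | 0.35 |
| 0.25, +0.05 | 0.592 | 0.591 | 0.608 | 0.588 | 1.6 | 0.48 |
| 0.25, +0.10 | 0.770 | 0.766 | 0.788 | 0.762 | 1.8 | 0.46 |
| 0.30, +0.05 | 0.583 | 0.580 | 0.607 | 0.576 | 2.4 | 0.58 |
| 0.30, +0.10 | 0.736 | 0.751 | 0.777 | 0.747 | 4.1 | 0.54 |

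Printed minus recomputed runs from −1.5 to +0.4 points in the Without column. In the With column it runs from +1.4 to +3.1 points, positive in all ten cells, with mean 2.3. The recomputed change due to curtailment is −0.4 to −0.1 points with ties credited, −0.1 to 0.0 with ties split, and +0.1 to +0.3 with ties counted wrong.

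**The case against.** **Simulation noise.** If the two columns came from separate runs of 2,500 trials, one printed gain has a standard error of 1.0 to 1.4 points, so a single cell can exceed its cap by chance. That stands. Ten of ten in one direction is harder to dismiss: the mean printed gain of 2.45 lies 4.7 standard errors above a uniform 0.6-point gain if the runs were independent, though less if cells shared random numbers.

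**The baseline.** Table A in Appendix VIII covers the same +0.10 configurations and prints 87%, 81%, 78%, 76% and 76%, up to 2.4 points from the Without column. Measured from Table A, the five gains become 0.5, 1.7, 3.4, 2.8 and 1.7 points. The 4.1 therefore rests partly on a low 0.736. All five still exceed their caps, and the excess of With over its recomputed value does not use the printed Without figures.

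**Incomplete reconstruction.** The written 0.85 drop rule gives 11% dropping at 0.10/0.10/0.20, where Table A prints 21%; the mean shortfall over 48 cells is 11.8 points. A fitted threshold of 0.75 recovers Table A's dropping column, and the With excess is then still 1.0 to 3.0 points (mean 2.2). Five readings of the stopping rule leave a mean excess of 2.0 to 3.3. Counting a tie at 35 as still leading raises the cap to 1.9, and 8 of 10 printed gains exceed it. The cause of the discrepancy cannot be determined from the documents.

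**One loose clause.** The surrounding text speaks of selection, and Section 10.3.2 plans an exact logistic regression comparing the arms. Neither changes the conclusion that Section 10.1.1 prescribes for a stopped trial. Appendix VIII does set a posterior criterion of 0.90 for a difference above 0.05, but in another setting: "If an arm is dropped after 60 patients, then we will compare the 2 remaining arms after each has 35 evaluable patients".

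**The 1.00 entries.** When all arms are equal any choice is correct, so 1.00 is right by definition. It is uninformative rather than wrong.

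**Conclusion.** Both parts hold, and both should be fixed. The rule justifies selecting Arm X early. It does not justify concluding that X's true rate is higher: at a minimum-lead stop of 8, 5 and 4 responders, the plan's own prior leaves 0.22 that another arm is best.

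The With column is not reproduced under the written rule. Its gains of 0.9 to 4.1 points compare with a cap of at most about 0.6, and its entries are roughly 1 to 3 points too high. The claim that correct selection is never decreased is unsupported, because the sign of the true change depends on a tie rule the plan does not state. The claim of minimal impact is supported.

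Confidence is medium. The table comparison assumes exactly 20, 27 and 35 per arm. It also rests on two inferences: that ties were credited to the best arm, and that 2,500 runs were used, the number given for Table A. The caps and conditional probabilities are exact enumerations and need neither inference; the caps ignore the first look and the drop rule, and with the drop rule included they are 0.1 to 0.5 points.

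**What to change.** 1. In Section 10.1.1, replace the conclusion clause with: *accrual stops and Arm X is selected as the winner; this does not establish that its true response rate is higher than those of the other two arms.*
2. Rerun the With column on the same simulated trials as the Without column, stating the tie rule, the number of runs and the Monte Carlo error.
3. Replace the statement that correct selection never decreases with the corrected figures, which should show a change of about half a point or less.
4. Minor: where the rule refers to the probability over a range of scenarios, say that it must exceed 0.90 in each of the four equal-rate cells, to match the closing paragraph of the rule.
5. Optional: print the equal-rate stopping probability in place of 1.00, and report each arm's response rate with a 95% interval and its posterior probability of being best.

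The cost is a few sentences and one short simulation. The stopping boundary, sample size and selected arm do not change.

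### The correct-selection probabilities in section 10.1.1 are too high for a rule that names one winner, and the gains shown for curtailment are not supported by the written rules

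*Combined protocol and SAP*

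**What the plan says.** Section 10.1 sets the final decision: "the regimen with the highest observed response rate (by central review of response) after one course of therapy will be selected", "provided that toxicity, tolerability, and other considerations confirm the feasibility of the regimen". It does not say what happens if two or three arms share the lead. Appendix VIII does not say how its simulations scored that event.

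Section 10.1.1 (Amendment 7A) adds early selection of a winner after 81 patients. The event it evaluates is a strict lead: "i.e. that the Arm X observed response rate would be greater than the observed response rates of other 2 arms". The trial continues if the conditional probability is "less than 0.90 for any one of the scenarios in which all 3 arms have the same true response rate".

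The supporting table gives the probability of correct selection with and without curtailment. It covers two inferior arms at 0.10 to 0.30 and a best arm 0, 5 or 10 points higher. The text introduces it with "The table below summarizes the minimal impact of incorporating stochastic curtailment at this stage" and adds "in none of these scenarios is the probability of correct selection decreased". The footnote reads "Probabilities of correct selection estimated by simulation, using same methods a results in the Appendix". No replicate count is given for this table; Appendix VIII A.3 gives 2,500 trials for Table A.

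**The concern.** In a selection design the probability of correct selection takes the place of power, and this table is the evidence offered for changing the design after the first interim look. Two features stand out.

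First, with 35 patients per arm and low response rates, ties for the lead are common, so the scoring of ties moves the figures by several points. Crediting every tie to the best arm is the most favourable scoring available.

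Second, the table shows curtailment raising correct selection in all ten cells with a true difference. Stopping at 81 rather than 105 patients uses less data, so a consistent gain is not expected. A reader would conclude that stopping early improves the selection by up to 4.1 points.

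**Working it through.** **Inputs.** Looks at 20 and 27 per arm and a final 35 per arm (section 10.1). Beta(0.2, 0.8) priors, the 0.05/0.85 drop rule and the 0.05/0.90 two-arm rule at 35 per arm, otherwise going to 42 (Appendix VIII). Curtailment at 0.90 in every equal-rate scenario (section 10.1.1). Assumption: 39 per remaining arm after a drop at the second look, from the total of about 105. The five zero-difference cells are 1.00 by definition and carry no information.

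**Step 1: exact sums at a fixed 35 per arm.** No drop, curtailment or simulation is involved. Let b(x) be the binomial probability of x responders on the best arm, and f(x) that on an inferior arm. Let G(x) be the probability that an inferior arm has fewer than x.

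- Strict win: S = Σ b·G²
- Tie for the lead with one other arm: T₂ = Σ 2b·G·f
- Three-way tie: T₃ = Σ b·f²
- Random tie-breaking: S + T₂/2 + T₃/3
- Every tie credited to the best arm: S + T₂ + T₃

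| Inferior rate, difference | Stated without | Stated with | Strict | Random | Ties credited |
|---|---|---|---|---|---|
| 0.10, +0.05 | 0.676 | 0.705 | 0.535 | 0.605 | 0.682 |
| 0.10, +0.10 | 0.855 | 0.875 | 0.759 | 0.806 | 0.856 |
| 0.15, +0.05 | 0.627 | 0.658 | 0.507 | 0.569 | 0.638 |
| 0.15, +0.10 | 0.818 | 0.827 | 0.717 | 0.764 | 0.814 |
| 0.20, +0.05 | 0.599 | 0.622 | 0.490 | 0.548 | 0.610 |
| 0.20, +0.10 | 0.780 | 0.814 | 0.689 | 0.736 | 0.785 |
| 0.25, +0.05 | 0.592 | 0.608 | 0.478 | 0.533 | 0.592 |
| 0.25, +0.10 | 0.770 | 0.788 | 0.670 | 0.716 | 0.764 |
| 0.30, +0.05 | 0.583 | 0.607 | 0.471 | 0.523 | 0.580 |
| 0.30, +0.10 | 0.736 | 0.777 | 0.656 | 0.702 | 0.749 |

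The best arm ties for the lead in 9 to 15% of trials (0.749 − 0.656 = 0.093; 0.682 − 0.535 = 0.147). Stated minus exact, in points:

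- Without curtailment: −1.3 to +0.6 with ties credited, +3.4 to +7.1 with random ties, +8.0 to +14.1 strict.
- With curtailment: +1.2 to +2.9 with ties credited, +6.3 to +10.0 with random ties.

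**Step 2: the full design** (400,000 simulated trials per cell, the same trials with and without curtailment). Stated minus recomputed, in points:

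- Without curtailment: −1.7 to +0.4 with ties credited, +2.9 to +7.0 random, +7.2 to +13.8 strict.
- With curtailment: +1.2 to +3.0 with ties credited, +5.9 to +9.9 random, +10.3 to +16.6 strict.

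The interim rules therefore hardly change the picture from Step 1. Six readings of the curtailment rule were tried. The stated with-curtailment values stay about 1 to 3 points above the highest ties-credited level from any of them.

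**Step 3: effect of curtailment on common trials.** Strict: +0.1 to +0.3 points. Random: −0.1 to 0.0. Ties credited: −0.5 to −0.1. The table displays +0.9 (0.827 − 0.818) to +4.1 (0.777 − 0.736).

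**Step 4: simulation noise.** For the largest excess over the exact ceiling, 0.814 − 0.7847 = 0.0293. At 2,500 trials SE = √(0.785 × 0.215 / 2,500) = 0.0082, and 0.0293/0.0082 = 3.6. Seven of the ten with-curtailment cells exceed the ceiling by more than 1.96 SE at 2,500 trials, two at 1,000 and none at 500.

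**Step 5: the section 10.5 target** (80% at a 15-point difference), exact at fixed 35. Over Table A's equal-arm rows (inferior rate 0.10 to 0.35), strict wins give 89.6% down to 79.9%. Random ties give 82.6% at their worst, near an inferior rate of 0.43.

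**The case against.** **The recomputation is not the sponsor's program.** This is fair. Simulating the written 0.05/0.85 rule gives only 50 to 85% of Table A's drop frequencies (10.5% against a stated 21% in one cell), so the two programs differ somewhere. That mismatch is a separate question. Step 1 uses no drop rule and gives the same result, so this point does not rest on it.

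**Noise may explain the with-curtailment column.** It may, if far fewer than 2,500 trials were run. Even at 2,500, if the two columns came from separate runs, five of the ten displayed gains are within 1.96 SE of zero. So an error in the sponsor's code is not shown. What stands is that the gains cannot be obtained from the written rules, and that the replicate count is missing.

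**Random tie-breaking is only one benchmark.** Ties might be settled by the toxicity and tolerability considerations in section 10.1. The achieved probability would then lie somewhere between strict and ties credited; reaching the top would require every tie to be settled in favour of the truly best arm. Exact ties also need equal denominators. The primary analysis is modified intent-to-treat, and "a maximum of 115 patients are anticipated to enroll to yield 105 eligible and evaluable patients". As an illustration only, with arms of 34, 35 and 36, averaged over the six assignments, the without-curtailment column is 3.2 to 6.9 points too high with no tie assumption needed.

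**The sentence that no scenario shows a decrease describes the table correctly.** It does. The recomputed shortfall is at most 0.5 points, is below the 0.7 to 1.0 point Monte Carlo SE at 2,500 trials, and reverses under strict wins.

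**A reader might infer that the trial is too small or that curtailment harms the selection.** Neither follows. The section 10.5 target survives random ties, and the recomputed effect of curtailment is close to nil.

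**Conclusion.** The point holds for the stated figures. The without-curtailment column is an upper bound that counts every tie as a correct pick; this scoring is inferred from the match, not stated. The column is about 3 to 7 points above random tie-breaking and 7 to 14 above strict wins. The with-curtailment column is about 6 to 10 points above random tie-breaking and about 1 to 3 above the upper bound in all ten cells, with a small replicate count as a possible explanation for the latter. The claim of minimal impact stands; the displayed gains do not.

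The sizing claim is not overturned. The 80% target holds under random ties. Under strict wins it is met or essentially met over Table A's equal-arm rows. Strict wins fall to 79.4% only near an inferior rate of 0.43, outside those rows.

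The conclusions assume looks at exactly 20, 27 and 35 per arm and 39 per arm after a second-look drop. The point should be fixed because these figures are the design's operating characteristics. No sample size or stopping decision depends on it.

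**What to change.** State in section 10.1 how a tie for the lead is resolved at final selection, for example at random or by the considerations already named there. Score ties in the simulations the same way. Rerun both columns of the 10.1.1 table on one common set of simulated trials, give the replicate count, and replace the figures and the sentence about no scenario being decreased with what the rerun shows. Restate the selection column of Table A in Appendix VIII on the same basis; over its 48 cells the stated values average 2.2 points above random ties and 0.1 below ties credited.

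The cost is one sentence on ties and a rerun of existing code. The stated figures would be a few points lower if ties are broken at random or not counted. Patients, sample size and stopping rules do not change.
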